Neurofilament light chain, inflammatory markers, calcitonin gene-related peptide, and kynurenone metabolites in patients with severe post- concussive symptoms

STATISTICAL ANALYSIS PLAN

NCT ID NOT YET ASSIGNED, FEBRUARY 28TH, 2023

[name]

Statistical analyses plan

At baseline (before randomization):

1) Concentration differences between groups

Concentration differences of biomarkers between patients and controls were assessed using two-way ANOVAs with gender and group (patient/control) as factors. This approach was used since gender differences are known for some biomarkers.

Before the test was conducted, normality was assessed using QQ-plots after log transformation and Barlett's test was used to test for equal variances. Interaction between group and gender was tested, and removed from the model if it was non-significant.

If statistical significantly differences were found, a post-hoc-analyses using Fisher's protected least-significant difference were conducted.

If Barlett's test showed unequal variances, a mixed model allowing for variance heterogeneity was used.

If data was not normally distributed, Kruskal Wallis test was used.

Neurofilament light chain was included as the primary outcome in this study since it is highly specific for brain tissue, and multiple studies have shown concentration differences between healthy controls and concussion patients.

Calcitonin-gene related peptide was included as a primary outcome as well (separate study) since it is related to headache.

2) Correlation between symptom score and biomarkers

The correlation between biomarkers and symptom score measured by the Rivermead Post Concussion Symptoms Questionnaire was tested by Spearman's Rank Correlation or Pearson correlation coefficient (depending on whether the data were normally distributed or not).

Neurofilament light chain and TNF-alfa were included as the primary outcomes since multiple previous studies have found an association.

At follow-up (after randomization):

1) To test whether the concentrations changed at follow-up, a paired t-test was used on all concussion patients regardless of the intervention (n=54). Before conducting the test, normality of the differences was assessed using QQ-plots, and variances were assessed using Bland Altman plots. If the data were not normally distributed or had unequal variance, a Wilcoxon signed-rank test was used.

2) To test whether the non-pharmacological intervention had an effect on the biomarkers, a two-way ANOVA on concentration differences (baseline – follow-up) was performed with gender and intervention arm as the two factors. This was included as a secondary outcome in the study, since we

did not believe that the biomarker change would be sensitive enough to detect changes in RPQ/psychology due to the non-pharmacological intervention.

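### The primary patient-control comparison is not randomised but adjusts for gender only; any age gap between the groups would enter the result if the biomarker varies with age

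*SAP*

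**What the plan says.** The comparison is in the SAP's first baseline item, under the heading "At baseline (before randomization"). Patients and controls are compared by "two-way ANOVAs with gender and group (patient/control) as factors". The reason given for gender is: "This approach was used since gender differences are known for some biomarkers". The interaction is dropped if it is not significant.

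The analysis scale appears to be logarithmic, since "normality was assessed using QQ-plots after log transformation". With unequal variances the SAP moves to a mixed model that allows for them, and names no further covariate. With non-normal data it moves to Kruskal-Wallis.

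On the outcome: "Neurofilament light chain was included as the primary outcome in this study". CGRP is also called primary, but for a separate study. Age is not mentioned anywhere in the SAP, whether as a covariate, a matching factor or part of a sensitivity analysis.

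**The concern.** Patients and controls differ by how they entered the study, so randomisation does nothing to make them alike in age. The SAP accepts that a personal characteristic related to biomarker level belongs in the model, and acts on this for gender alone. Because the model's terms are all named, this is a choice of analysis and not a detail left open: run as written, the analysis leaves any age difference in the group effect.

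Two consequences follow if the biomarker varies with age:

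- **Bias.** An age gap could produce an apparent group difference, or hide a real one, in the primary comparison. A larger sample does not reduce this bias.
- **Precision.** Even with no gap, age-related variation stays in the error term and lowers power.

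The fallbacks do not repair this. Kruskal-Wallis as planned takes no covariate, so it loses the gender adjustment as well.

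**Working it through.** The SAP gives no control count, effect size, SD, significance level or power for this comparison, so there is no figure of its own to reproduce. The check shows the mechanism and its size over a stated range.

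**Inputs**

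- Patients: 54. The SAP gives this for the follow-up paired test on "all concussion patients regardless of the intervention (n=54"); using it at baseline is an assumption.
- Assumed, not in the SAP: 40 controls, age SD 12 years in each group, residual SD 0.4 on the log scale, biomarker slope of 0 to 0.03 log units (about 0-3%) per year of age, two-sided 5% test.

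**Formulas** (normal approximation)

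- SD with age omitted = √(0.4² + (12 × slope)²)
- r = 12 × slope / SD
- Bias in log units = slope × gap. In within-group SDs this is r × d, with d = gap/12.
- SE = SD × √(1/54 + 1/40) = SD × 0.2086
- False-positive rate = Φ(bias/SE − 1.96) + Φ(−bias/SE − 1.96)

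**Age gap of 6 years (d = 0.5), no true group difference, age omitted**

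| Slope per year | SD | r | Bias (log) | Apparent difference | Bias/SE | False-positive rate |
|---|---|---|---|---|---|---|
| 0 | 0.400 | 0 | 0 | 0% | 0 | 5.0% |
| 0.01 | 0.418 | 0.29 | 0.06 | 6% | 0.69 | 10.6% |
| 0.02 | 0.466 | 0.51 | 0.12 | 13% | 1.23 | 23.4% |
| 0.03 | 0.538 | 0.67 | 0.18 | 20% | 1.60 | 36.1% |

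Simulations of the same scenarios (4,000 replicates each) gave 10-11% at the 0.01 slope and 34-36% at the 0.03 slope. With age in the model they gave 5% within simulation error.

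**Smaller gaps.** For slopes from 0.01 to 0.03, the same formula gives 5.6% to 8.3% at 2 years and 7.5% to 18.8% at 4 years.

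**No gap: precision only.** For a true log difference of 0.25, power with age omitted is Φ(0.25/SE − 1.96): 82%, 73% and 61% at slopes of 0.01, 0.02 and 0.03. With age included the SD is 0.4 and power is Φ(0.25/0.0834 − 1.96) = 85%. Simulation put the figures 1-2 points lower (about 81%, 72% and 60%, against 83-84%). In general, with balanced ages, the adjusted model needs a fraction 1 − r² of the sample: 96% at r = 0.2, 91% at r = 0.3 and 75% at r = 0.5.

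**Cost of adjusting when ages differ.** Age is then partly collinear with group, and the variance of the group effect is multiplied by 1 + p·q·d², with p·q = (54 × 40)/94² = 0.244. At a 6-year gap this is 1 + 0.244 × 0.25 = 1.06. If the slope is in fact zero, power then falls from 85% to 83%. At a 12-year gap the factor is 1.24 and power is 77%.

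**The case against.** The strongest reply has three parts.

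- **The premise is not in the SAP.** It mentions gender differences in biomarkers and says nothing about age. This stands. The association has to be treated as an assumption, and the range must include zero, where there is no bias.
- **The bias needs an age gap, and nobody has shown one.** Recruitment and matching of controls are normally described in the protocol, which is not at hand. This also stands. If controls were matched on age, most of the bias goes and only precision is left.
- **The larger figures depend on steep assumptions.** About 35% false positives, or power of about 60%, needs r of about 0.67. At r of about 0.29 and no gap, only some 3 points of power are lost. With a weak correlation and a sizeable gap the power gain can vanish: in a separate calculation with 54 per group, 80% without age became 79.2% with age at r = 0.2 and d = 0.5. The bias is therefore the stronger argument.

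A reader might infer that the NfL result is already confounded by age, or that adjustment is free apart from one degree of freedom. The documents support neither. They contain no age data, and adjustment carries the collinearity cost shown above.

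The reply leaves the main point untouched. The analysis model belongs in the SAP, this one is complete and omits age, and it would offer no protection if a gap were present.

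**Conclusion.** The point holds in conditional form. The primary baseline comparison for NfL (and for CGRP in the separate study) is not randomised and is adjusted for gender only, with one fallback that adjusts for nothing. If age is related to the biomarker, a gap of d age-SDs biases the group effect by about r×d within-group SDs. At an assumed 6-year gap, the false-positive rate runs from the nominal 5% when there is no association, through about 11% at r of about 0.29, to about 35% at r of about 0.67. With balanced or matched ages the issue is one of efficiency only, and minor when r is 0.2-0.3.

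All these sizes rest on assumed values, including the control count and the use of the follow-up n at baseline. They are not estimates for this trial. The change is worth making because it is cheap protection for the primary result, not because an error in that result has been shown.

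**What to change.** - Make the primary model a linear model on log concentration with group, gender and age (continuous). Report the adjusted geometric mean ratio, patients over controls, with its 95% CI.
- Keep the two-factor ANOVA as a sensitivity analysis.
- State that age and gender are both carried into the unequal-variance model.
- Replace Kruskal-Wallis with a fallback that takes covariates, such as the same model with robust or bootstrap standard errors, or the same model on ranks.
- The SAP is written in the past tense. If the data have already been analysed, add the age-adjusted model as a labelled amendment and report it beside the planned one.

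The cost is a change of wording, one covariate that is routinely recorded, one degree of freedom, and an assumed log-linear age effect that can be checked on a residual plot. If ages differ between groups there is also modest variance inflation, about 6% at a 6-year gap under the assumed inputs.

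### Bartlett's test decides whether the primary patient-control comparison allows unequal variances; if group sizes are clearly unequal, a missed difference in spread moves the test off its nominal level, in either direction

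*SAP*

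**What the plan says.** Under the heading for baseline (before randomization), item 1, biomarker differences between patients and controls are "assessed using two-way ANOVAs with gender and group (patient/control) as factors". Two checks come before the test: "normality was assessed using QQ-plots after log transformation", and Bartlett's "test was used to test for equal variances". Each has its own consequence. If Bartlett's "test showed unequal variances, a mixed model allowing for variance heterogeneity was used". Separately, "If data was not normally distributed, Kruskal Wallis test was used".

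The rule applies to the main comparison: "Neurofilament light chain was included as the primary outcome in this study", and CGRP is named as primary for a separate study.

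The SAP does not state the number of controls, any SD, the level of the group test or the level of Bartlett's test. The only count is 54 concussion patients, given for the paired comparison at follow-up.

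**The concern.** The ordinary ANOVA pools the residual variance over patients and controls. If the two groups differ in spread and in size, the pooled standard error of the group difference is wrong. It is too small when the smaller group is the more variable one and too large when it is the less variable one.

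The Bartlett step is meant to catch this, but with one modest group it often misses a moderate difference in spread. The ANOVA is then kept in trials where its standard error is wrong. The false-positive rate of the NfL comparison, or its power in the opposite case, comes to depend on a weak preliminary test. The SAP already names a model that does not have this problem, but uses it only after a significant Bartlett result.

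**Working it through.** The SAP gives no power or error figure to reproduce, so the check asks how the stated rule behaves when there is no group difference.

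**Inputs.** From the SAP: the two-way ANOVA, the Bartlett step, the heterogeneous-variance fallback and 54 patients (the follow-up count, assumed to hold at baseline). Assumed: analysis of normal log concentrations, a 5% level for both tests, no gender interaction, 15 to 108 controls, and a control/patient SD ratio k from 0.5 to 2. The fallback is taken as separate residual variances for patients and controls with Satterthwaite degrees of freedom.

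**Step 1: how far the pooled test is off.** Ignore gender. Let patients have SD 1, controls SD k, and let m be the number of controls.

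- True variance of the difference: V = 1/54 + k²/m
- Variance the ANOVA estimates on average: E = [(53 + (m − 1)k²)/(52 + m)] × (1/54 + 1/m)
- Approximate actual level: 2[1 − Φ(1.96/√(V/E))]

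Results:

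- m = 27, k = 1.25: V = 0.01852 + 0.05787 = 0.07639; E = (93.625/79) × 0.05556 = 0.06584; √(V/E) = 1.077; level about 6.9% (simulated 6.7%).
- m = 27, k = 0.8: V = 0.01852 + 0.02370 = 0.04222; E = (69.64/79) × 0.05556 = 0.04897; √(V/E) = 0.929; level about 3.5% (simulated 3.5%).
- m = 40, k = 1.25: V = 0.05758; E = 0.05390; √(V/E) = 1.034; level about 5.8% (simulated 5.8%).
- m = 54: V = E for any k, so the level is about 5%.

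**Step 2: the whole rule, simulated.** Bartlett was run on the two groups, with the ANOVA after a non-significant result and the unequal-variance model after a significant one (40,000 to 150,000 runs per setting).

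| Controls | k (control/patient SD) | Bartlett detects | ANOVA rejects after a miss | Whole rule rejects |
|---|---|---|---|---|
| 15 | 1.5 | not shown | 12.4% | 7.6% |
| 15 | 0.67 | not shown | 1.6% | 3.8% |
| 27 | 1.25 | 26% | 7.0% | 5.9% |
| 27 | 1.5 | 65% | 9.5% | 5.8% |
| 27 | 0.8 | 24% | 3.6% | 4.2% |
| 27 | 0.67 | 65% | 3.1% | 4.5% |
| 40 | 1.25 | 32% | 6.0% | 5.4% |
| 40 | 0.8 | 31% | 4.4% | 4.6% |
| 45 | 0.67 | 79% | 5.0% | 4.8% |
| 108 | 0.8 | 47% | 6.8% | 5.5% |

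With 54 controls the whole rule rejects in 4.7 to 5.1% of trials.

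The last two columns differ because detections dilute the error. At 27 controls and k = 1.25, misses contribute 0.737 × 6.97% = 5.14 points of the 5.94% total. Detected trials add the other 0.80.

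**Step 3: sensitivity to how Bartlett is run.** The SAP does not say whether it is applied to the two groups or to the four group-by-gender cells. Over four cells it detects less and the distortion grows. At 27 controls and k = 1.25, detection falls to 17% and the whole rule rejects in 6.4%. In a separate four-cell simulation (75% women, 20,000 runs) the whole rule rejected, for k = 1.25 and 1.5, in 7.8% and 8.8% with 15 controls, 6.7% and 7.6% with 20, and 6.1% and 6.1% with 30. At k = 0.67 it rejected in 2.9 to 4.1% over the same control counts.

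**Step 4: without the pre-test.** The unequal-variance model used from the start rejected in 4.7 to 5.3% of trials in every setting of step 2. Across all the simulations run, the range was 4.6 to 5.6%.

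**The case against.** The strongest case against is that the SAP does check variances and does name a valid remedy, and that nothing in it shows this study is affected. The control count may be fixed in the protocol, which is not at hand. With 40 to 54 controls the rule is harmless for practical purposes. The relevant error rate is that of the whole rule, not the rate after a miss, and at 27 controls with Bartlett on two groups it is only 4.2 to 5.9%. The figures near 9% need about 15 controls. All of this stands, and it makes the point an inexpensive improvement rather than an error that invalidates the comparison.

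Three stronger readings are tempting and not supported.

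- *The test is off its level whenever controls are fewer than patients.* It is not: at 45 controls and k = 0.67 the ANOVA after a miss is at 5.0%. The condition is also incomplete, since a clearly larger control group matters slightly too (5.5% with 108 controls when patients vary more).
- *Bartlett's sensitivity to non-normality does further damage.* With equal variances and heavy-tailed or mildly lognormal data it flags in 17 to 20% of trials. A false flag, however, only sends the marker to the unequal-variance model, and the whole rule still rejects in 4.8 to 5.3% (20 to 40 controls).
- *The two fallback rules contradict each other.* The SAP gives no order between them, but a natural reading sends non-normal markers to Kruskal-Wallis. Stating the order would add a missing detail. Its absence is not a contradiction.

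**Conclusion.** The point holds in a conditional form. If group sizes are clearly unequal, letting Bartlett's test choose the model leaves the primary NfL group test off its nominal level. It is liberal if the smaller group varies more and conservative, with lost power, if it varies less.

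With 54 patients, normal log data, a 5% level and a moderate difference in spread, the two-stage rule rejects in roughly 6 to 9% of null trials in the liberal direction, or 3 to 5% in the conservative direction, with 15 to 30 controls. With 40 to 54 controls it rejects in about 5%. The distortion is greatest with the fewest controls and with Bartlett run over four cells.

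The control count, SDs and levels are assumptions, so these figures are a range of possibilities and not an estimate of the error in this study. The change is worth making because the better model is already in the SAP and costs little.

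**What to change.** In baseline item 1, drop Bartlett's test as the rule for choosing the model. State that log concentration is analysed from the start with group and gender as factors, separate residual variances for patients and controls, and Satterthwaite or Kenward-Roger degrees of freedom. Report the group SDs descriptively.

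Keep the stated non-normality rule, and say that it is the only fallback and applies to markers that remain non-normal after log transformation. This also settles the order of the rules. It does not make Kruskal-Wallis robust to unequal spread: in simulations with 15 to 30 controls it rejected in 6.3 to 9.9% of null trials at SD ratios of 1.5 to 1.75. Results reached by that route should be read with the group SDs beside them.

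The change is a short edit to the SAP and needs no new data. The statistical cost is a small loss of power if variances are truly equal and controls are few. For a 0.6 SD difference it is about 2.4 percentage points with 15 controls, 1.4 with 20, 0.4 with 30 and none with 54.

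### If the data are non-normal, the baseline patient-control comparison falls back to Kruskal-Wallis, which has no gender adjustment although the SAP says gender is needed

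*SAP*

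**What the plan says.** All but the last item below come from the SAP, At baseline, item 1 (Concentration differences between groups).

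- The main analysis is "two-way ANOVAs with gender and group (patient/control) as factors". The reason given is "This approach was used since gender differences are known for some biomarkers".
- The interaction is handled by a rule: "Interaction between group and gender was tested, and removed from the model if it was non-significant".
- The check that decides the branch is visual: "normality was assessed using QQ-plots after log transformation". No criterion is given.
- If variances are unequal, "a mixed model allowing for variance heterogeneity was used". A model of that kind can keep both factors.
- If normality fails, "If data was not normally distributed, Kruskal Wallis test was used". The grouping variable is not named, and no stratification or within-gender testing is mentioned. The SAP does not say whether its post-hoc step (Fisher's protected LSD) follows this test.
- On the outcome: "Neurofilament light chain was included as the primary outcome in this study since it is highly specific for brain tissue".
- At follow-up, item 2, the comparison of intervention arms "was performed with gender and intervention arm as the two factors".

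**The concern.** The SAP's reason for including gender is that some biomarkers differ between women and men. That reason does not depend on the shape of the distribution, so it still applies when the data turn out non-normal. The fallback nevertheless moves to a test with a single grouping factor, so the gender adjustment and the interaction test are both lost.

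Patients and controls are not randomised to their groups, so nothing in this document makes their gender mix equal. If the mix differs and the biomarker differs by gender, an unadjusted rank test can report a gender difference as a patient-control difference, or hide a real one. In addition, biomarkers that pass the QQ-plot check get a gender-adjusted comparison and those that fail do not. Results within one study would then answer different questions.

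**Working it through.** The SAP gives no sample size, power or effect size for this comparison, so there is no figure of its own to reproduce. The check has a textual part and a numerical part.

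**1. What Kruskal-Wallis can test here.** There are two possible readings.

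- *Two groups (patient, control).* The statistic ranks all subjects together and compares rank sums. Gender does not enter.
- *Four cells (gender by group).* The null hypothesis is that all four distributions are equal. A gender difference alone makes it false, so a significant result does not isolate the group effect, and there is no interaction test.

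**2. Size of the confounding under the two-group reading.** The shift in the mean difference is the gender effect times the difference in the share of women. With 40 of 54 patients women (0.741) and a gender effect of 0.8 SD:

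- 50% women among controls: 0.8 × (0.741 − 0.500) = 0.19 SD
- 65% women among controls: 0.8 × (0.741 − 0.650) = 0.07 SD

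**3. Simulation.** The only input from the SAP is 54 patients, a number it states for follow-up. The assumptions are: 40 women and 14 men among patients; 27 or 54 controls; t(3) errors scaled to SD 1; gender shift 0.3, 0.5 or 0.8 SD; two-sided alpha 0.05; 10,000 runs per setting. The Monte Carlo standard error at 5% is √(0.05 × 0.95 / 10,000) = 0.2 points.

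The comparator is the van Elteren test, z = T/√V. Over gender strata k:

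- T = Σ w_k [R_k − n_1k(N_k + 1)/2], with w_k = 1/(N_k + 1)
- V = Σ w_k² n_1k n_0k s_k² / N_k

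R_k is the patients' rank sum within gender k, n_1k and n_0k are the numbers of patients and controls, N_k is their sum, and s_k² is the variance of the ranks.

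False positives (%) of the two-group Kruskal-Wallis test with no true group difference, for gender shifts of 0.3 / 0.5 / 0.8 SD:

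| Women among controls | 27 controls | 54 controls |
|---|---|---|
| 50% | 6.4 / 8.3 / 11.5 | 7.6 / 11.8 / 19.7 |
| 60% | 5.6 / 5.9 / 6.5 | 5.5 / 6.9 / 9.0 |
| 65% | 4.5 / 4.4 / 3.5 | 4.9 / 5.0 / 5.1 |
| 75% (equal mix) | 4.5 / 3.7 / 3.2 | 4.6 / 4.1 / 3.3 |

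Van Elteren lies between 4.5% and 5.6% in all of these settings.

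Power (%) for a true difference of 0.5 SD, Kruskal-Wallis vs van Elteren:

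| Women among controls, gender effect | 27 controls | 54 controls |
|---|---|---|
| 50%, 0.8 SD opposing the group effect | 32.2 vs 78.0 | 43.1 vs 91.7 |
| 65%, 0.8 SD opposing the group effect | 58.8 vs 79.9 | 73.4 vs 92.7 |
| 75% (equal mix), 0.8 SD | 71.6 vs 80.3 | 88.7 vs 93.3 |
| 75% (equal mix), none | 80.4 vs 79.8 | 93.8 vs 93.6 |
| 50%, none | 80.6 vs 77.8 | 93.9 vs 92.0 |

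Under the four-cell reading, the omnibus test rejected in 22.7% to 99.6% of runs from gender alone. If within-gender Wilcoxon tests follow a significant omnibus result, a false patient-control claim occurs in 5.8% to 9.7%.

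**4. Sensitivity to the assumed mix.** A second set of assumptions used 54 patients and 54 controls with 2,000 runs. The two-group false-positive rate was 9% (70% vs 50% women, 0.5 SD), 17% (70% vs 50%, 1 SD), 17% (80% vs 50%, 0.5 SD) and 40% (80% vs 50%, 1 SD). Van Elteren stayed at 4% to 5% in these settings.

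**The case against.** The strongest reply is that the SAP does not name the grouping. A k-sample test next to a gender-by-group design with LSD follow-up could well mean four cells, and then gender is not literally dropped. That is fair, and the four-cell rejection rate is not a patient-control error rate. The 5.8% to 9.7% is ordinary multiplicity from two uncorrected tests, bounded by 1 − 0.95² = 9.75%. But this reading still yields no gender-adjusted group test, so it does not rescue the sentence.

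Second, bias under the two-group reading needs three conditions together: data judged non-normal, a gender effect on that biomarker, and unequal gender mix. The document establishes none of them for neurofilament light chain, and any matching of controls may be in the protocol. This stands, and it limits the claim to a possible bias. With equal mix and a 0.3 SD gender effect even the power loss is negligible: 80.0% vs 81.5% with 27 controls, 93.1% vs 93.4% with 54.

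Third, the opposing-direction power figures show one side only. With 65% women among 54 controls and the gender effect reversed, Kruskal-Wallis reaches 94.2% against 92.4%. That is true, but the gain is itself confounding.

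Fourth, the follow-up analysis is a main model and so is an imperfect comparator for a fallback. That is fair; the point does not depend on it.

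Last, other methods would also keep gender: aligned-rank or rank-based two-factor models, or bootstrap or permutation versions of the two-way model. Some of them retain the interaction test, which van Elteren does not. That is a choice among remedies, not a defence of the present text.

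**Conclusion.** The concern holds. In the non-normal branch the SAP offers no gender-adjusted patient-control comparison under either reading of the sentence, although its own reason for adjusting still applies. That much follows from the text alone.

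The size of the harm is conditional. Under the stated assumptions, false positives range from slightly below nominal (equal or near-equal mix) to about 20% (75% vs 50% women, 0.8 SD gender effect, 54 controls). With equal mix there is no false-positive problem. The cost is then power: about 9 points with 27 controls (80.3 − 71.6 = 8.7) and 5 points with 54 (93.3 − 88.7 = 4.6) at the largest gender effect considered. These are ranges, not estimates for this study, because the SAP gives neither the gender mix nor the number of controls. The correction should be made, since the branch can decide the primary outcome and the repair is cheap.

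**What to change.** Replace the Kruskal-Wallis sentence with one named method, for example:

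> If the log-transformed data are not normally distributed, patients and controls are compared with a gender-stratified Wilcoxon (van Elteren) test; the Wilcoxon result and Hodges-Lehmann difference within each gender are reported alongside.

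This is one sentence and needs no new data. Any biomarker already analysed with Kruskal-Wallis would have to be re-run. If gender has no effect, the power cost is under 1 point with equal mix and 2 to 3 points at 75% vs 50% women (80.6 − 77.8 = 2.8; 93.9 − 92.0 = 1.9).

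Two limits remain. This branch would have no formal group-by-gender interaction test, and opposite effects in women and men can cancel in the stratified statistic. The within-gender results are reported for that reason; the stratified test should carry the patient-control conclusion.

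### Both follow-up analyses use only patients sampled twice, and n=54 is not defined as the number entered or the number of pairs; if samples are missing, selective loss can bias them

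*SAP*

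**What the plan says.** Under the SAP heading on follow-up, item 1 asks whether concentrations changed: "a paired t-test was used on all concussion patients regardless of the intervention (n=54"). Its fallback is also a paired method: "If the data were not normally distributed or had unequal variance, a Wilcoxon signed-rank test was used". Item 2 asks whether the intervention affected the biomarkers: "a two-way ANOVA on concentration differences (baseline – follow-up) was performed with gender and intervention arm as the two factors". Item 2 is ranked as secondary ("This was included as a secondary outcome in the study, since we" …). Item 1 is not ranked.

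The only mixed model in the SAP belongs to the baseline patient–control comparison, as a response to unequal variances. Neither follow-up item uses the baseline value of a patient who was not sampled again.

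**The concern.** A paired t-test, a signed-rank test and an ANOVA on differences are all undefined for a patient with one sample. The choice of method therefore restricts both follow-up questions to complete pairs, even though the missing patients' baseline concentrations have been measured.

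If patients with high baseline values are lost more often, those retained start below the mean of everyone who entered. Their follow-up values regress towards that mean, and item 1 reads the drift as a rise over time. In item 2 the drift cancels between arms if loss works the same way in both. If it does not, it enters the arm effect, and item 2 is the only randomised comparison in this SAP.

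The figure of 54 does not settle whether this matters, because the SAP does not say what it counts.

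**Working it through.** **The plan's figure.** The SAP gives no derivation of 54, so there is nothing to reproduce. It fits two readings:
- If 54 entered, losses of 10/20/30% leave 54 × 0.9 = 48.6, 54 × 0.8 = 43.2 and 54 × 0.7 = 37.8 pairs on average.
- If 54 is the number of pairs, the same losses mean 54/0.9 = 60, 54/0.8 = 67.5 (68) and 54/0.7 = 77.1 (78) entered.

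**Inputs.** Only 54 comes from the SAP. The rest are assumptions: equal SDs at both visits (set to 1), no true change, loss related to baseline only, two-sided 5% test, visit correlation ρ of 0.5 to 0.9, N starters of 60, 68 or 80, and a gap g of 0.5 or 0.8 SD between lost and retained patients at baseline.

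**Item 1.**
1. Retained patients' baseline mean lies (N − 54)/N × g below that of all starters.
2. Bias in mean change = (1 − ρ) × (N − 54)/N × g.
3. Standard error of the paired mean ≈ √(2(1 − ρ)/54). At ρ = 0.5 this is √(1/54) = 0.136.
4. The false-positive rate follows from the noncentral t distribution with 53 degrees of freedom and noncentrality bias/SE.

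Example: N = 80, g = 0.8, ρ = 0.5. The shift is 26/80 × 0.8 = 0.26 SD, the bias 0.5 × 0.26 = 0.13 SD, the noncentrality 0.13/0.136 = 0.955, and the false-positive rate 15.5%.

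Results at ρ = 0.5:

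| Starters | Lost | g = 0.5: bias (SD), false positives | g = 0.8: bias (SD), false positives |
|---|---|---|---|
| 60 | 6 | 0.025, 5.4% | 0.040, 6.0% |
| 68 | 14 | 0.051, 6.6% | 0.082, 9.1% |
| 80 | 26 | 0.081, 9.0% | 0.130, 15.5% |

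Direct simulation of these six cells (40,000 runs each) agreed to within 0.7 percentage points; the last cell gave 16.2%. For N = 80 and g = 0.8, the formula gives 11.2% at ρ = 0.7 and 7.0% at ρ = 0.9.

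**Keeping all baselines.** The maximum-likelihood estimate of mean change takes the completers' follow-up mean, adds the regression slope times (baseline mean of all − baseline mean of completers), and subtracts the baseline mean of all. In the same simulations its bias was about 0, with a false-positive rate of about 5%.

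**Item 2.** A second simulation took 54 entered, ρ = 0.5, and log-odds of loss changing by 1 per SD of baseline.
- Same pattern in both arms: bias in the arm difference was at most 0.003 SD.
- Opposite patterns in the two arms: bias was 0.090/0.169/0.255 SD at 10/20/30% loss. At 20% this is about twice the item 1 bias in that simulation (2 × 0.085 = 0.170).
- Opposite patterns at ρ = 0.9: 0.019/0.034/0.051 SD.
- Adjusting completers for baseline reduced the bias to at most 0.010 SD throughout.

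**The case against.** The strongest objection is that the SAP shows no loss. It mentions no withdrawal, missed sample or larger number entered, and those counts may stand in a protocol that is not at hand. A reader might infer that the 54 are completers under a wrong label. The document does not support that: the phrase "all concussion patients regardless of the intervention (n=54") mainly says that the arms are pooled, and 54 may be everyone. This stands, so the bias is conditional. It does not remove the point, because the methods are fixed in the SAP and none of them can use an unpaired patient.

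A reader might also infer that stopping the intervention removes a patient. Nothing says so. Someone who stops but gives the second sample has a pair and stays in both items.

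Nor does baseline-dependent loss by itself bias both items. Item 1 also needs change to be related to baseline, and for very stable biomarkers the bias is small. Item 2 needs the pattern to differ by arm, and opposite patterns are an extreme case.

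Finally, the large figures need heavy loss: 15–16% requires 26 of 80 lost, a 0.8 SD gap and the lowest correlation together. With 6 of 60 lost, inflation is negligible. Item 2 is secondary, and the outcomes named as primary stand under the baseline headings, which this point does not touch.

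**Conclusion.** The point holds in conditional form. Both follow-up analyses are complete-pair by construction, and the SAP leaves 54 undefined. If any patient lacks a follow-up sample, item 1 describes completers and can show a false change when loss depends on baseline and change is related to baseline. Item 2 is at risk only from a loss pattern that differs by arm.

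Under the stated assumptions the damage to item 1 runs from negligible at about 10% loss to roughly a tripling of the 5% error rate at about one third lost (26/80 = 32.5%). The documents do not show where in that range the trial lies, or that it lies there at all. The change is still worth making because it costs little and, if no sample is missing, leaves the item 1 estimate unchanged on the same scale.

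**What to change.** 1. Define 54, and report how many patients entered, how many gave both samples, and the baseline levels of those with and without a second sample.
2. Replace the two main analyses by one likelihood-based repeated-measures model: both visits as outcomes, log scale, unstructured covariance, every randomised patient with a baseline sample, in the arm randomised.
3. Include visit, gender, gender-by-visit and arm-by-visit terms, with a common baseline mean across arms. Gender-by-visit is needed because a gender main effect cancels from the change, so it alone would not reproduce item 2's adjustment.
4. Read item 1 from the visit contrast averaged over arms, weighted by the numbers randomised. The plain visit coefficient will not do: under reference coding it is the change in one arm. Read item 2 from the arm-by-visit effect.
5. Keep the paired t-test or Wilcoxon test, labelled as patients with both samples, as a sensitivity analysis and as the fallback if log-scale normality fails.

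The cost is SAP wording and modest programming; no new samples or patients are needed. The model assumes data missing at random given baseline, gender and arm, and is slightly less simple to report. The common baseline mean also makes item 2 a baseline-adjusted comparison, so its estimate can differ somewhat from the change-score ANOVA even with complete data.
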